2.1 Analysis Populations

2.1.1 Intention-to-treat Population (ITT)

The ITT population will include all randomized participants, including those who are later found not to meet study eligibility criteria. There were two participants who mistakenly “re-joined” the trial after infusions ended and were re-randomized in a second site, near their original site. The detail for the two participants is in Appendix II. They will only be counted once in the ITT population. Their data from the 2nd randomization will not be included in the analysis.

2.1.2 Modified Intention-to-treat Infusion Population (mITT)

All participants in the ITT population who have completed at least one infusion will be included in the modified intention-to-treat population. The mITT population will be the primary analysis population.

2.2 Data Sources

The data used for analysis will come from 5 sources: the randomization data from the Interactive Voice/Web System (IXRS), the e-CRF data collected by the iMedidata Rave electronic data capture system (RAVE), the adjudicated endpoint data from the clinical events committee database (CEC), the site-level information stored in the Clinical Trial Management System (CTMS) database, and the CDC National Death Index (NDI).

Masked-source NDI search results will be used to focus a search for supporting clinical and other documentation. If supporting documentation is obtained, the data will be submitted to the CEC process prior to being used in the analysis. If needed, a Mortality Review Committee will be assigned to classify potential death events when there are insufficient/incomplete or contradictory NDI and/or Call Center data to make a reliable determination. Additional details will be described in a separate charter.

2.3 General Analysis Conventions

Statistical comparisons will be performed using two-sided significance tests. An alpha level of 0.05 will determine significance unless otherwise specified.

Continuous variables will be presented in terms of percentiles (e.g., median, 25th percentile, and 75th percentiles) along with means and standard deviations. Categorical variables will be summarized in terms of frequencies and percentages.

All programs written to create analysis datasets or perform analyses will be validated according to SOPs by the Statistical Programming group.

All statistical analysis will be performed using SAS® v9.4 or higher (Cary, NC USA) and/or other proper software, e. g. R.

2.4 Disposition of Participants

Disposition of participants (number randomized, number who received treatment, number of infusions received per patient, number of withdrawals and dropouts from the study, number lost to follow-up, length of follow-up, time since last contact, number unmasked) will be summarized by active chelation vs placebo chelation groups using a CONSORT flow diagram and subject disposition table.

Lost to follow-up among alive and non-withdrawn participants will be reported in the CONSORT diagram as described above. The number of participants lost to follow-up with a primary endpoint will be included in the total and also reported separately. Participants alive and not withdrawn or lost to follow-up will be defined as completing the study.

The definition for lost to follow-up will be:

No contact within 12 months of the end of study. End of study is defined as the 5-year informed consent expiration date or administrative end of study date (June 30, 2023). Last contact is defined as the last known alive date.

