3.1 General

3.1.1 Estimands and Censoring Scheme

Summaries of the descriptions of the estimand attributes and censoring schemes are shown in **Table 3**. Like TACT, the primary analysis will include all identified events obtained as part of the planned follow-up from infusion visits and call center interviews.

Table 3. Key Study Estimands and Censoring Scheme.

Objective Description / Study Population	Endpoint	Summary statistics	Events to be included in the endpoint derivation	Censoring date
Primary Objective/ mITT	Time from randomization to the first occurrence of primary composite endpoint of all-cause mortality, MI, stroke, coronary revascularization, or hospitalization for unstable angina	Hazard ratio estimate based on a Cox proportional hazards model.	All positively adjudicated primary endpoint events post-randomization except those occurring after withdrawal of consent or ICF expiration. Events occurring after withdrawal consent or ICF expiration will be censored. Subjects with events after withdrawal or ICF expiration will be censored at the min(date withdrew consent, date of last contact with patient/proxy where event status was assessed).	Among subjects not experiencing endpoint of interest: Censoring date = min(date withdrew consent, date of last contact with patient/proxy where event status was assessed) Date of last contact defined as: If the last contact occurred during the study infusion phase - use last infusion visit date where survival status and event status were assessed (yes or no to event). If last contact occurred during call center follow up period – use ‘complete’/‘incomplete’ status date by patient/proxy where survival status and hospitalization status were assessed (yes or no to hospitalization).

				For composite endpoints, date of last assessment = the earliest of the last assessment date among all components.
Secondary Objective / mITT	Overall rate of recurrent events due to all-cause mortality, MI, stroke, coronary revascularization, or hospitalization for unstable angina	Hazard ratio estimate based on a proportional intensity model by Andersen-Gill and a marginal model by Wei, Lin and Weissfeld.	*same as primary endpoint	*same as primary endpoint

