Secondary Objective / mITT	Time from randomization to the first occurrence of the secondary composite endpoint of cardiovascular mortality, MI, or stroke	Cause specific hazard ratio estimate based on a cause-specific Cox proportional hazards model.	All positively adjudicated endpoint events post-randomization except those occurring after withdrawal of consent or ICF expiration date. Non-CV death or undetermined cause of death is considered a competing risk. Among subjects experiencing competing risk (non-CV death or undetermined death is a competing risk of CV death or MI/stroke if a subject died without having any	Among subjects not experiencing endpoint of interest or competing event: Censoring date = min(date withdraw consent, date of last contact with patient/proxy where event status was assessed) *Date of last contact defined in 1 st row, 5 th column (primary endpoint)

			
of these events beforehand):
 
Event date = non-CV or undetermined death date;
	
Secondary Objective / mITT	Time from randomization to all-cause mortality	Hazard ratio estimate based on a Cox proportional hazards model.	
All deaths post-randomization (including adjudicated deaths obtained from the NDI search)
 
A death date after withdrawn consent or ICF expiration (obtained from public data source) is considered an event.
	
Among subjects who are alive:
 
Censoring date = (date last known alive)
 
Date of last known alive defined as:
 
If the last contact occurred during the study infusion phase - use last infusion visit date.
 
If last contact occurred during call center follow up period – use ‘complete’/‘incomplete’ status date by patient/proxy or (‘not done’ status date where source = patient) or last alive date from Call Center where death status was assessed.

Secondary Objective / mITT	Total number of SAE and percentage of patients experiencing at least 1 SAE.	Number and proportions by treatment group. Confidence intervals will be based on the Miettinen-Nurminen method.	Randomization to min(withdraw consent, 30 days post final infusion)	N/A

Sensitivity Analysis of the Primary Outcome / Bayesian analysis using TACT results as one of the priors / mITT	*Same as primary analysis	Treatment effect mean posterior hazard ratio based on a Bayesian time to event model	*Same as primary analysis	*Same as primary analysis

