Another sensitivity analysis is planned to assess how the primary analysis would be affected by various assumptions regarding the occurrence of primary endpoint events among those who withdrew consent or were lost to follow-up, as was performed and published in TACT. Baseline characteristics by treatment group will be assessed for the patients who did versus did not withdraw consent or were lost to follow-up. Events will be imputed by simulation only for the consent withdrawal or lost patients who did not have a documented occurrence of one of the primary events prior to the withdrawn consent/lost to follow-up. The different percentages of the withdrawn or lost patients will be assumed to have an event at their censoring time. The event rates among patients that withdrew or were lost to follow-up in each treatment group will be varied across a broad spectrum and include scenarios that were markedly unfavorable to chelation. The imputed event rates for patients who withdrew consent or were lost to follow-up will be combined with the observed event rates of patients who completed the study to assess the treatment effect via a hazard ratio. These analyses will focus on scenarios in which events among withdrawn or lost patients in the active arm are assumed to occur at a higher rate than withdrawn or lost patients in the placebo arm.

Another sensitivity analysis is planned for the primary endpoint to censor, at the point of last contact, those deaths that were identified more than one year following the most recent study contact.

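### Loss to follow-up is defined by the last known alive date, so patients whose event status was not assessed can count as completers and fall outside the imputation sensitivity analysis of the primary endpoint

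*SAP*

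**What the plan says.** SAP 2.4 defines lost to follow-up as "No contact within 12 months of the end of study" and then fixes the date to be used: "Last contact is defined as the last known alive date". The remaining patients are settled by one sentence: "Participants alive and not withdrawn or lost to follow-up will be defined as completing the study". The SAP gives no other definition of loss to follow-up.

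Table 3 in SAP 3.1.1 works with two different dates:

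- **Primary endpoint.** Event-free patients are censored at consent withdrawal or, if earlier, at the "date of last contact with patient/proxy where event status was assessed". For a composite, this is the earliest of the last assessment dates of its components.
- **All-cause mortality.** Survivors are censored at the date last known alive. During call-center follow-up, that date can also come from a call logged as not done with the patient as source, or from a "last alive date from Call Center where death status was assessed". Neither requires MI, stroke or hospitalization status.

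SAP 3.2.2 limits the missing-data analysis of the primary endpoint: "Events will be imputed by simulation only for the consent withdrawal or lost patients who did not have a documented occurrence" of a primary event before withdrawal or loss. Table 3 repeats the restriction to withdrawn or lost patients.

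**The concern.** The date that suits mortality decides who counts as having missing data for a composite that is mostly non-fatal in kind. A patient can be censored early for the primary endpoint because nobody established event status, yet be reported as a completer because someone established that the patient was alive. The sensitivity analysis that tests the result against missing primary-endpoint data then omits a group whose primary-endpoint data are missing.

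Two outputs are at stake. The completion figure in the CONSORT diagram may overstate how completely the primary endpoint was observed. The imputation analysis may also look more reassuring than its coverage justifies.

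**Working it through.** **1. One patient traced through the rules.** Take a patient last assessed for events early in follow-up, later only known to be alive, and last known alive within 12 months of end of study.

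- SAP 2.4: contact falls within 12 months, so not lost; alive and not withdrawn, so a completer.
- Table 3, primary row: censored at the early assessment.
- SAP 3.2.2: neither withdrawn nor lost, so no event is imputed.

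The 12-month allowance has a similar effect by itself. After month 12, calls are every 4 months (SAP 1.1), so the allowance spans 12 / 4 = 3 call intervals.

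**2. How long a gap the rules permit.** Enrollment closed on December 31, 2020 (Protocol 3) and the administrative end is June 30, 2023 (SAP 2.4), which gives 2.5 years for the last patient and up to 5 years for others. If event status was last assessed at about week 40 (0.77 years), the gap could be 2.5 − 0.77 = 1.7 years up to 5 − 0.77 = 4.2 years. This shows what the rules allow, not what happened.

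**3. The plan's event rate reproduced.** SAP Appendix I projects 137 + 39 = 176 patients with an event over 1990 patient-years: 176 / 1990 = 8.8% per patient-year. Its other scenarios are 6.9% and 9.1%.

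**4. Illustrative size.** The composite rate includes death, and a patient known alive at the end of a gap did not die during it. With n patients, gap g years, rate r and a share d of first events that are deaths:

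expected unobserved non-fatal first events = n × (1 − exp(−g × r × (1 − d)))

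The values n = 50, g = 2 and d = 20 to 40% are assumptions; the documents give none of them.

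- r = 0.088, d = 0.20: 50 × (1 − exp(−0.1408)) = 6.6
- r = 0.088, d = 0.40: 50 × (1 − exp(−0.1056)) = 5.0
- Lowest, r = 0.069, d = 0.40: 50 × (1 − exp(−0.0828)) = 4.0
- Highest, r = 0.091, d = 0.20: 50 × (1 − exp(−0.1456)) = 6.8

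These totals cover both arms together. Leaving deaths in the rate would give 50 × (1 − exp(−0.176)) = 8.1, which is too many for patients known to be alive.

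**The case against.** The strongest reply is that little depends on this. Several parts of it stand.

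- **The primary analysis gives no false credit.** A reader might infer that the hazard ratio is computed with unassessed time counted as event-free. Table 3 does not support that: such patients are censored at their last event-status assessment.
- **Later events are not lost.** Table 3 counts all positively adjudicated events except those after consent withdrawal or consent expiry, so an event found after the last assessed contact still enters the analysis. Deaths can also surface through the National Death Index and the adjudication process (SAP 2.2).
- **Long gaps may be rare.** The schedule in Protocol 6.1 collects hospitalization and mortality at every call, and Table 3 accepts incomplete calls if both survival and hospitalization status were obtained. The two dates separate only when hospitalization status was not obtained.
- **Bias is not shown.** A reader might set the missing events against the number of extra active-arm events that would overturn a significant result. The two are not comparable: the first is a total over both arms, and only a difference between arms could move the estimate. Nothing in the documents points to differential assessment in this double-blind trial with centralized calls.

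Two further replies do not close the gap. SAP 3.2.2 also censors deaths identified more than one year after the last contact (Table 3 words this for all adjudicated events). That removes recorded events and does nothing for unassessed patients with none. SAP 2.4 also reports time since last contact, but that section equates last contact with last known alive, so the figure need not reveal missing event assessment.

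**Conclusion.** The mismatch is real on the wording of the SAP. Loss to follow-up rests on vital status, primary-endpoint censoring rests on event-status assessment, and the imputation set follows the first. Some patients with unobserved primary-endpoint time can therefore be counted as complete and left out of the analysis meant to test the effect of missing data. SAP 2.4 does not refer to the mortality row of Table 3, but it uses the same term and the SAP offers no other meaning for it.

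The consequence is confined to the completion count and the coverage of one sensitivity analysis. The number of patients affected is unknown. The illustration of about 5 to 7 events rests on an assumed headcount, gap and death share. It must not be read as an estimate of events missed in this trial, or as evidence that the treatment effect is biased. The change is worth making because it uses dates that the censoring rules already require.

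**What to change.** - For the primary endpoint, define incomplete follow-up by the event-status assessment date in the primary row of Table 3. Keep the last known alive definition for mortality only.
- Keep withdrawn and lost patients in the imputation analysis of SAP 3.2.2, and add event-free patients whose event-status assessment ends before their end of study by more than one scheduled call interval (4 months plus a stated window). Including every patient censored before end of study would sweep in ordinary gaps between calls and make the set meaningless.
- Let the imputed risk reflect the length of unassessed time, and exclude death for any period in which the patient is known to have been alive.
- Report observed over planned event-assessed person-time by arm.
- State in SAP 2.4 which end-of-study date applies when consent expiry and June 30, 2023 differ, since the gap is measured from it.

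The cost is revised SAP wording, some programming, a larger imputation set and a less favourable completion figure. No new data are needed, and the primary analysis does not change.

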2.5 Demographic and Baseline Characteristics

Demographic and baseline characteristics will be summarized by active and placebo chelation groups and for the overall MITT population. These include cardiovascular risk factors, comorbidities, relevant descriptors from the history, concomitant medical care including post-MI medications, treatments for diabetes, over-the-counter supplements and herbal remedies. Physical examination, laboratory data, cardiopulmonary symptoms, and past clinical events. Blood and urine metals pre- and post-chelation are discussed in the SAP for the Trace Metals Biorepository Core Lab.

2.6 Handling of Missing Data

Every effort will be made to obtain complete data during the course of the trial. If missing data remains despite all the efforts, rules on how to handle the missing data will be implemented.

If the proportion of subjects with missing values in any of the covariates for the primary analysis, i.e. age, sex, and baseline insulin use, is greater than 1%, then the missing values will be imputed to the mode.

Since the clinical endpoints are adjudicated by the CEC, we don't anticipate missing values for positively adjudicated outcomes. In the very rare occasion where the event day is missing, it will be imputed as the last day of the month. If missing day and month, then December 31st of the provided year will be used. If the year is missing, no imputation will be performed.

3 Analysis of Clinical Endpoints

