SEP 12, 2023	2.2 Data sources, 2.6 Missing data, 3.1.1 Estimands and censoring, 3.2.1 Primary Analysis, 3.2.2, Sensitivity, 3.3.1 Recurrent events, 3.4 Subgroup analyses, Appendix III	Added NDI as a data source. Updated imputation for missing data. Added sensitivity analyses. Added hierarchy for formal hypothesis testing. Added event rate equation for recurrent event analysis. Updated subgroup analyses. Added Bayesian sensitivity analysis.	Additional information on NDI. Missing dates in the data. Additional sensitivity analyses requested. Requests from PIs.

6 Appendices

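### Incomplete event dates are set to month end or December 31 with no upper bound, so the exclusion after withdrawal or consent expiry could drop an adjudicated event known to precede that cut-off

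*SAP*

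**What the plan says.** SAP 2.6 has three rules for incomplete event dates:

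- Day missing: "In the very rare occasion where the event day is missing, it will be imputed as the last day of the month".
- Day and month missing: "If missing day and month, then December 31st of the provided year will be used".
- Year missing: "If the year is missing, no imputation will be performed".

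None of them mentions death, withdrawal, ICF expiration, the reporting contact or the end of the study as a limit. The same section says "we don't anticipate missing values for positively adjudicated outcomes". The revision log (SAP section 5, September 12, 2023) records that the imputation rules were updated, and lists "Missing dates in the data" among the reasons.

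For the primary endpoint, Table 3 (SAP 3.1.1) says "Events occurring after withdrawal consent or ICF expiration will be censored". Such participants are censored at the earlier of withdrawal and the last contact at which event status was assessed. Section 3.2.1 repeats the exclusion. In Table 3 the recurrent-event endpoint takes over the primary rule, and the composite of CV death, MI or stroke has the same two cut-offs. All-cause mortality differs: deaths after withdrawal or ICF expiration count.

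The date June 30, 2023 appears in SAP 2.4, where it helps to define loss to follow-up. Appendix I plans database lock for October 2023.

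**The concern.** Each rule is workable alone; the problem is how they combine. The imputation always picks the latest date that fits the partial record, and the exclusion looks for events that are too late. If the second rule is run on the output of the first, an event can fail only because its date was filled in. Section 3.1.1 intends the primary analysis to include all events identified through planned follow-up, so such a loss would go against the plan's own aim.

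ICF expiration is not an unusual cut-off. Follow-up stops at five years, and the power simulations in Appendix I assume no re-consent after that.

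There are side effects. The sensitivity analysis for withdrawn and lost participants (3.2.2) imputes events only for those without a documented event beforehand, so a real event moved past withdrawal would make the participant look event-free. A late date can also push an event past the one-year window in another Table 3 sensitivity analysis.

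**Working it through.** **The plan's event target.** Inputs: HR 0.70, two-sided alpha 0.05, 85% power, 1:1 allocation (protocol 9.2 and Table 3). The Schoenfeld formula gives 4 × (1.960 + 1.036)² / (ln 0.70)² = 282.3, which agrees with the stated 282. Power with 282 events is Φ(√282/2 × 0.3567 − 1.960) = Φ(1.035) = 85.0%.

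**Size of the shift.** For a true date spread evenly over a 365-day year, December 31 is later by 364/2 = 182 days on average (maximum 364). Month end is later by the sum over months of m(m − 1)/2, divided by 365, where m is the days in the month: 5,373/365 = 14.7 days (maximum 30).

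**Event and cut-off in the same calendar year, event on or before cut-off.** There are 365 × 366/2 = 66,795 such date pairs.

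- Year only known: the imputed date passes the cut-off unless the cut-off is itself December 31 (365 pairs). So (66,795 − 365)/66,795 = 99.5% are lost.
- Day missing: loss requires event and cut-off in the same month. So 5,373/66,795 = 8.0% are lost.

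**By time from event to cut-off** (all cut-off dates over four years, 2019–2022):

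| Gap (days) | Lost, year only | Lost, day missing |
|---|---|---|
| 7 | 98% | 74% |
| 30 | 92% | 0% |
| 90 | 75% | 0% |
| 180 | 50% | 0% |
| 365 | 0% | 0% |

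If events are spread evenly over the five years (1,826 days) before the cut-off, the loss is 182/1,826 = 10.0% of year-only dates and 14.7/1,826 = 0.8% of day-missing dates.

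**Example.** A participant withdraws on October 15, 2021. An adjudicated MI, reported before withdrawal, is dated only 2021. It is imputed to December 31, 2021, 77 days after withdrawal. If that date governs inclusion, the MI is removed and, with no other qualifying event, the participant is censored.

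**How common the ICF cut-off is.** Assuming even enrollment over 4.25 years ending December 31, 2020, those randomized more than 2.5 years before that end reach five years by June 30, 2023: (4.25 − 2.5)/4.25 = 41%.

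**Effect on power.** The documents give no count of incomplete dates, so the losses below are assumptions, with the HR held at 0.70. Each lost event is 1/282 = 0.35% of the target.

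| Events lost | Events left | Power |
|---|---|---|
| 0 | 282 | 85.0% |
| 1 | 281 | 84.8% |
| 3 | 279 | 84.6% |
| 5 | 277 | 84.3% |
| 10 | 272 | 83.7% |

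**Impossible dates among retained events.** A year-only 2023 event becomes December 31, 2023, after both June 30, 2023 and the planned October 2023 lock. A participant randomized in 2019 or 2020 who has not withdrawn keeps the event at that date. A non-fatal event can also be dated after death. In the recurrent-event model that is an impossible order. In the CV composite, SAP 3.3.2 censors at a non-CV or undetermined death with no prior composite event, so an MI or stroke dated after such a death would be lost.

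**The case against.** The strongest reply is that the SAP never says the imputed date decides inclusion. Table 3 excludes events that occurred after the cut-off, and an event reported before withdrawal plainly did not. A sensible programmer might retain it. That stands: the loss is conditional on one implementation. But the SAP states no order of operations, and running the two rules in sequence as written produces the loss.

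The second reply is rarity. Endpoints are adjudicated, and the SAP calls a missing day very rare. The revision log gives no count and does not separate day-missing from year-only dates, so it shows that the problem arose without contradicting that statement. The rules are also the same in both arms, and nothing in the documents points to a difference between arms.

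Three stronger readings are tempting but not supported:

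- A reader might infer that events dated after the study end are also dropped. Table 3 and 3.2.1 name only withdrawal and ICF expiration; June 30, 2023 serves to define loss to follow-up. A late-2023 date is implausible but does not exclude the event unless one of those two cut-offs comes first.
- A reader might infer that an MI dated after death costs the participant's primary event. It does not, because an eligible death is itself a component and counts on its own date.
- A reader might conclude that month-end imputation is itself an error. Latest date or midpoint is a choice of convention; the missing bound is the fault.

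**Conclusion.** The point holds as a gap in the rules with a small expected effect. Uncapped latest-date imputation, combined with the exclusion after withdrawal or ICF expiration, can remove adjudicated events known to precede the cut-off from the primary, recurrent-event and CV-composite analyses, provided the exclusion is run on imputed dates. Loss is nearly certain for a year-only date with the cut-off later in the same year, and possible for a day-missing date with the cut-off in the same month. Separately, retained events may carry dates after the planned lock or after death; the latter matters for the recurrent-event and CV-composite analyses. All-cause mortality does not lose events this way.

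The number affected is unknown. If it is 1 to 5 events, power falls by 0.2 to 0.7 percentage points. No bias between arms is shown. This is a low-priority correction, worth making because it is cheap and avoids discarding confirmed events.

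**What to change.** Amend SAP 2.6 and cross-refer from Table 3:

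1. Decide inclusion from what is known before imputation. For example, an event reported at a contact before withdrawal or ICF expiration is included. This step must come first: capping every imputed date at the cut-off without it could bring in events that truly occurred afterwards, which Table 3 means to exclude.
2. Then impute within the recorded month or year, bounded below by randomization and the last event-free contact, and above by the earliest of the reporting contact, death and, for events known to precede them, withdrawal or ICF expiration. Midpoint or latest date within those bounds is optional.
3. Report the number of imputed event dates by arm, split by day missing and by day and month missing.

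After month 12, calls are scheduled every four months (SAP 1.1), so contact dates should usually narrow the interval well below a calendar year. The cost is a short SAP amendment and some extra programming to bring in contact dates. No new data collection is needed.
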